11.5. Index Procedure

The preparation of the subject for the percutaneous procedure will be performed following standard techniques. Refer to the Lotus Valve System DFU for detailed instructions about preparation and placement of the Lotus Valve.

It is recommended that a stiff guidewire (e.g., Safari) is used during the Lotus Valve implant procedure.

11.6. Post-procedure / Prior to Hospital Discharge

The subject may be discharged from the hospital when clinically stable, at the Investigator's discretion per local standard of care. Prior to discharge from the hospital, the following data is to be collected:

- Complete safety event assessment, including any SAE that led to death, ADE, SADE, USADE, device deficiency with associated treatment, and any VARC event regardless of seriousness and device relationship.
- Per the expert consensus document on TAVI, antiplatelet therapy with aspirin and a thienopyridine is recommended to decrease the risk of thrombotic or thromboembolic complications if there are no contraindications to these medications⁴³. Subjects should be treated with aspirin and clopidogrel for at least 1 month following valve implantation. Subsequent antiplatelet therapy should be at the investigator's discretion, or in accordance with country-specific labeling for the medications. If oral anti-coagulation is indicated after valve implantation, antiplatelet therapy should consist of either aspirin or thienopyridine. Combination treatment with oral anti-coagulation and dual antiplatelet therapy after valve implantation should be avoided.
- Underlying heart rhythm
- NYHA classification

- TTE, including assessment of effective orifice area, peak systolic and mean aortic valve gradient pressure, aortic regurgitation assessment, mitral regurgitation, LVEF, left ventricular end-diastolic and end-systolic diameter, TR jet velocity and LA volume, per local standard of care. A pre-discharge TTE for subjects implanted with a Lotus Valve must be sent to the Echocardiography Core Laboratory for independent analysis.

Prior to discharge, clinical staff should review the study follow-up visit schedule with the subject to maximize follow-up compliance.

11.7. Follow-up

All implanted subjects enrolled in the main cohort of 1000 subjects will be evaluated at 30 days, 1, 2, 3, 4 and 5 years post index procedure. Follow-up visit at 1 year post valve implantation should be conducted via outpatient clinic visit. Follow-up visits at 30 days and 2 through 5 years may be conducted in person (preferred) and via telephone interview. Subjects with no Lotus Valve implanted will be followed for safety through 30 days after the initial attempted index procedure.

The additional cohort of approximately 80 subjects will be contacted for follow up at 30 days post valve implantation.

It is important that the follow-up visit schedule be maintained as closely as possible for all subjects. Boston Scientific recognizes that subjects may not be able to return for all scheduled visits at precisely the date required, and therefore, a period of time in which each visit should be conducted is indicated in Table 11.1-1. Each follow-up visit must be performed by trained study personnel. Data from collected tests and images as well as medical assessments will be recorded in source documentation and captured in the eCRFs.

In the event that study personnel learn of a subject's hospitalization outside the study center, the center should make every effort to obtain copies of reports or results based on tests (e.g., echocardiogram) and/or procedures performed on the study subject.

11.7.1. 30-Day Follow-up (30±7 days)

All enrolled subjects must be evaluated 30 days after the index procedure. The 30-day follow-up visit may be conducted in person (preferred) or via telephone interview. During the 30-day follow-up, the following assessments are to be collected:

- Complete safety event assessment, including any SAE that led to death, ADE, SADE, USADE, device deficiencies with associated treatment, and any VARC events regardless of seriousness and device relationship.
- All antiplatelet and other cardiovascular medications administered in accordance with society guidelines⁴³ and local standard of care. Subjects should be treated with aspirin and clopidogrel for at least 1 month following valve implantation. Subsequent antiplatelet therapy should be at the investigator's discretion, or in accordance with country-specific labeling for the medications. If oral anti-coagulation is indicated after valve implantation, antiplatelet therapy should consist of either aspirin or thienopyridine. Combination

treatment with oral anti-coagulation and dual antiplatelet therapy after valve implantation should be avoided.

- Underlying heart rhythm, including assessment of pacemaker dependency for subjects who had a pacemaker implanted after the index procedure.
- NYHA classification
- TTE, including assessment of effective orifice area, peak systolic and mean aortic valve gradient pressure, aortic regurgitation assessment, mitral regurgitation, LVEF, left ventricular end-diastolic and end-systolic diameter, TR jet velocity and LA volume, per local standard of care.
- EQ-5D Quality of Life Questionnaire during office visit or via mail.

11.7.2. Annual Follow-up (± 45 days)

All implanted subjects enrolled in the main cohort of 1000 subjects will be evaluated at 1, 2, 3, 4 and 5 years after the index procedure. Follow-up visit at 1 year post valve implantation should be conducted via outpatient clinic visit. Annual follow-up visits at 2 through 5 years may be conducted in person (preferred) or via telephone interview. During annual follow-up, the following assessments are to be collected:

- Complete safety event assessment, including any SAE that led to death, ADE, SADE, USADE, device deficiencies with associated treatment, and any VARC events regardless of seriousness and device relationship.
- All antiplatelet and other cardiovascular medications administered in accordance with society guidelines⁴³ and local standard of care.
- Underlying heart rhythm, including assessment of pacemaker dependency for subjects who had a pacemaker implanted after the index procedure.
- NYHA classification
- TTE, including assessment of effective orifice area, peak systolic and mean aortic valve gradient pressure, aortic regurgitation assessment, mitral regurgitation, LVEF, left ventricular end-diastolic and end-systolic diameter, TR jet velocity and LA volume, per local standard of care. A TTE performed 1 year after valve implantation must be sent to the Echocardiography Core Laboratory for independent analysis.
- EQ-5D Quality of Life Questionnaire during office visit or via mail at 1 year, 3 year and 5 year follow-up.

11.8. *Withdrawal and Replacement of Subjects*

Subjects may withdraw from the study at any time, with or without reason and without prejudice to further treatment. Withdrawn subjects will not undergo any additional study follow-up, nor will they be replaced. The reason for withdrawal will be recorded (if given) in all cases of withdrawal. The investigator may discontinue a subject from participation in the study if the investigator feels that the subject can no longer fully comply with the requirements of the study or if any of the study procedures are deemed potentially harmful to the subject. Data that have already been collected on withdrawn subjects will be retained and used for analysis but no new data will be collected after withdrawal.

11.9. Study Completion

All implanted subjects enrolled in the main cohort of 1000 subjects will be followed for the duration of 5 years post index procedure. A subject's participation in the study will conclude after completion of the 5 year follow-up visit.

For subjects enrolled in the additional 80-subject cohort, participation in the study will conclude after completion of the 30-day follow-up visit.

12. Statistical Considerations

12.1. Endpoints

12.1.1. Primary Endpoint (Main Cohort)

The study is powered to assess one primary endpoint, which is all-cause mortality at 30 days post implant as assessed by an independent CEC. The null and alternative hypotheses for the primary device performance endpoint are as follows.

$$H_0: \text{Mortality}_{30D} \geq \text{PG}$$

$$H_1: \text{Mortality}_{30D} < \text{PG}$$

where Mortality_{30D} is the 30-day all-cause mortality rate for the Lotus Valve and PG is 14%.

A one-sample exact binominal test will be used to test the one-sided hypothesis. The all-cause mortality at 1 year post implant will be summarized using descriptive statistics.

12.1.1.1. Hypothesis (Main Cohort)

All-cause mortality at 30 days post implant procedure is less than the PG of 14 % (expected rate of 10% + testing margin of 4%)

12.1.1.2. Sample Size – Primary Endpoint (Main Cohort)

The sample size calculation for the primary endpoint is based on the following assumptions:

- Expected 30-day all-cause mortality rate = 10%
- Performance goal (PG) = 14% (expected rate of 10% + testing margin of 4%)
- Test significance level (α) = 0.025 (1-sided)
- Power ($1 - \beta$) > 95%
- Planned enrollment of up to 1000 subjects
- Two planned interim analyses on the primary endpoint at 30 days post-implant procedure will be performed on the first 250 and 500 subjects enrolled. A final analysis will be performed on all enrolled subjects
- The primary analysis population for the primary endpoint will be the subject population attempted or implanted with the Lotus Valve.

Note: The expected 30-day all-cause mortality rate is assumed to be 10% based on a literature review of studies evaluating the Medtronic CoreValve System and the Edwards Lifesciences SAPIEN Transcatheter Heart Valve System (FRANCE 2 registry³⁶).

Note: The alpha-level for the interim and final analyses is adjusted using the Pocock alpha spending function⁵⁰ (see Section 12.3.2).

12.1.2. Secondary Endpoint (Main Cohort)

The study is powered to assess one secondary endpoint, which is grade of paravalvular aortic valve regurgitation pre-discharge as assessed by TTE post valve implantation. The null and alternative hypotheses for the primary device performance endpoint are as follows.

$$H_0: AR_{\text{pre-discharge}} \geq PG$$

$$H_1: AR_{\text{pre-discharge}} < PG$$

where $AR_{\text{pre-discharge}}$ is the proportion of subjects with moderate/severe aortic regurgitation pre-discharge post implant procedure for the Lotus Valve and PG is 16.5%.

A one-sample exact binominal test will be used to test the one-sided hypothesis.

12.1.2.1. Hypothesis (Main Cohort)

Proportion of subjects with moderate/severe aortic regurgitation pre-discharge as assessed by TTE post implant procedure is less than the PG of 16.5%.

12.1.2.2. Sample Size – Secondary Endpoint (Main Cohort)

The sample size calculation for the secondary endpoint is based on the following assumptions:

- Expected proportion of subjects with moderate/severe aortic regurgitation pre-discharge as assessed by TTE post valve implantation = 10%
- Performance goal (PG) = 16.5% (based on FRANCE 2 registry³⁶)
- Test significance level (α) = 0.025 (1-sided)
- Power ($1 - \beta$) > 99%
- Planned enrollment of up to 1000 subjects
- Two planned interim analyses on the secondary endpoint prior to discharge from the hospital post-implant procedure will be performed on the first 250 and 500 subjects enrolled. A final analysis will be performed on all enrolled subjects.
- The primary analysis population for the secondary endpoint will be the subject population implanted with the Lotus Valve.

Note: The performance goal is set at 16.5% based on rates observed with Medtronic CoreValve System and the Edwards Lifesciences SAPIEN Transcatheter Heart Valve System (FRANCE 2 registry).

Note: The alpha-level for the interim and final analyses is adjusted using the Pocock alpha spending function (see Section 12.3.2).

12.1.3. Statistical Methods

All subjects who are enrolled will be eligible for evaluation. Handling of dropouts and missing data will depend on their frequency and the nature of the outcome measure. The distribution of prognostic factors between subjects with and without data will be examined. Methods to eliminate or minimize bias will be implemented and described completely. Statistical models that account for censored data will be employed in appropriate circumstances (e.g., for time-to-event outcomes). Sensitivity analyses, including a tipping-point analysis for the primary endpoint, will be conducted to assess the impact of different assumptions on interpretation of the results. Outlier values will be evaluated for their validity. Suspected invalid data will be queried and corrected in the database prior to statistical analysis.

The data of the additional cohort of approximately 80 subjects will be summarized using descriptive statistics and will not be pooled with the first cohort of 1,000 subjects in the data analysis. No statistical hypotheses will be tested in the additional cohort.

12.2. General Statistical Methods

12.2.1. Analysis Sets

The primary endpoint will be evaluated on an ITT basis (all subjects enrolled, whether or not a study device is implanted). For the ITT analysis, all subjects who sign the written ICF and are enrolled in the study will be included in the analysis sample, regardless of whether the study device was implanted.

The primary analysis population for the secondary endpoint will be the subject population implanted with the Lotus Valve (as-treated subject population).

12.2.2. Control of Systematic Error/Bias

The selection of patients will be made from the Investigator's usual case load. All subjects who have signed the ICF and are selected to receive a Lotus Valve will be enrolled in the study. The study center's heart team assessments and imaging measurements before device placement will contribute to the determination of subject eligibility for the study.

12.3. Data Analyses

Baseline and outcome variables will be summarized using descriptive statistics for continuous variables (mean, standard deviation, number of observations, minimum and maximum) and discrete variables (percentage and count/sample).

12.3.1. Risk Adjusted Analysis

Risk adjusted clinical outcomes by valve size will be analyzed on the subject population implanted with the Lotus Valve (as-treated subject population).

12.3.2. Interim Analyses

Two interim analyses for the primary and secondary endpoints will be conducted on the first 250 and 500 subjects, and a final analysis will be conducted on the planned 1000 subjects of the main cohort. The Pocock alpha spending function⁵⁰ is used to adjust the alpha-level for each analysis: 0.00894, 0.00895, and 0.01301, respectively. If the *P* value from the one-sample exact binominal test is $< \alpha$, the Lotus Valve will be concluded to have event rate $< PG$. This corresponds to the one-sided Clopper-Pearson upper $(1-\alpha)\%$ confidence bound of the observed event rate being $< PG$.

The two planned interim analyses are pre-specified to provide a formal hypothesis testing approach to examine the primary and secondary endpoints with the adjusted significance level. There is no plan to stop the subject enrollment even if the null hypothesis is rejected at each of the two planned interim analyses.

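### The mortality and regurgitation goals are each tested at the full one-sided 0.025 with no testing order; a mortality-first sequence would cut the worst-case chance of a false claim from about 4.2% to at most about 2.2%, at a stated cost in regurgitation power.

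*Combined protocol and SAP*

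**What the plan says.** The main cohort carries two formal hypotheses.

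- **Mortality (sections 12.1.1 to 12.1.1.2).** 30-day all-cause mortality is tested against a goal of 14%, with 10% expected and power above 95%. The level is listed as "Test significance level (α) = 0.025 (1-sided".
- **Regurgitation (sections 12.1.2 to 12.1.2.2).** The text states "The study is powered to assess one secondary endpoint". Pre-discharge moderate/severe regurgitation is tested against a goal of 16.5%, with 10% expected and power above 99%. One-sided 0.025 is listed again.

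On timing, section 12.3.2 says "Two interim analyses for the primary and secondary endpoints will be conducted on the first 250 and 500 subjects", followed by a final analysis at 1000. The levels are 0.00894, 0.00895 and 0.01301. When the exact binomial P value is below the level for that look, "the Lotus Valve will be concluded to have event rate" below the goal. The Success Criteria in the synopsis repeat this. The section describes the interim looks as formal hypothesis tests of both endpoints and says that enrolment continues after a rejection.

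No testing order, gatekeeping rule or split of alpha between the two endpoints appears in the supplied text. The words primary and secondary are the only ranking, and no testing rule is attached to them.

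**The concern.** The plan adjusts for three looks within each endpoint but is silent about the two endpoints together. The regurgitation test is not merely descriptive: it has its own goal, alpha, power and success rule. The study can therefore make either of two formal claims, each with its own 2.5% allowance.

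Two things are at stake. One is the study-wide chance of a false claim. The other is what a reader should make of a regurgitation success when mortality has not met its goal, or has not met it yet. The second situation is likely. At the planning rates, and with independent endpoints, the chance that the first look shows regurgitation success without mortality success is 0.708 × (1 − 0.306) = 49%. The chance that this is the position by the second look is 0.969 × (1 − 0.625) = 36%. Those would be true claims, but the plan does not say how they rank.

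**Working it through.** **Inputs.** Sections 12.1.1.2 and 12.1.2.2 give goals of 14% and 16.5%, an expected rate of 10% for each endpoint, and one-sided 0.025 for each. Section 12.3.2 gives looks at 250, 500 and 1000 and the three levels. Assumptions of this check: every subject is evaluable for both endpoints, and the endpoints are independent unless stated otherwise.

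**Step 1: reproduce the plan's figures.** Pocock-type spending is 0.025 × ln(1 + (e − 1)t). At t = 0.25, 0.5 and 1 it gives cumulative spend of 0.00893, 0.01550 and 0.025, and nominal levels of 0.00893, 0.00895 and 0.01300. These match the plan to rounding.

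The rejection limit at each look is the largest count whose exact binomial P value is below the level. An exact recursion over the three looks then gives:

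| | Limits at 250/500/1000 | Type I error at the goal | Power at a true 10% |
|---|---|---|---|
| Mortality (goal 14%) | 22/51/115 | 2.19% | 95.14% |
| Regurgitation (goal 16.5%) | 27/62/138 | 2.03% | 99.995% |

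Both stated powers (above 95% and above 99%) are confirmed.

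**Step 2: chance of at least one false claim when both nulls hold.**

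- Independent endpoints: 1 − (1 − 0.02192)(1 − 0.02027) = 0.0417.
- Any dependence: at most 0.02192 + 0.02027 = 0.0422.
- Simulation at patient-level correlation −0.1, 0.1, 0.3 and 0.5: 4.19%, 4.15%, 4.08% and 3.92%.
- Nominal levels, independent: 1 − 0.975² = 4.94%.
- If only 80% to 95% of subjects are evaluable for regurgitation (an assumed range; the plan gives no figure): 4.2% to 4.5%, independent.

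If only one null is true, the error is 2.19% or 2.03%, already within 2.5%.

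**Step 3: mortality-first sequence.** If the mortality null is true, any false claim requires mortality to be rejected first, so the error is at most 2.19%. If only the regurgitation null is true, it is at most 2.03%. The study-wide error is therefore at most about 2.2%.

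**Step 4: cost at the planning rates.**

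- Mortality power is unchanged at 95.14%.
- A formal regurgitation claim now needs both rejections: 0.95142 × 0.99995 = 0.9514. Regurgitation must now cross at or after the look at which mortality does. This makes no visible difference, because the final look alone has power 0.99995 for regurgitation. The chance of winning both is therefore the same with or without the sequence.
- The chance of a regurgitation claim by look 1 falls from 70.8% to at most 30.6%, and by look 2 from 96.9% to at most 62.5%. The ceilings are the mortality rejection probabilities.

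With regurgitation at 10%, power for the regurgitation claim depends on true mortality:

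| True 30-day mortality | Power for a formal regurgitation claim |
|---|---|
| 9% | 99.7% |
| 10% | 95.1% |
| 11% | 73.5% |
| 12% | 36.9% |

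At the 1.7% reported for the 60-subject REPRISE II cohort (section 4.2.1.2), mortality power is essentially 100% and the loss is negligible.

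**Step 5: alternative.** Halving every level for both endpoints would keep regurgitation power at 99.98% but cut mortality power to 91.0%, below the stated 95%.

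**The case against.** The strongest reply is that no stated rule is broken. The 0.025 is given separately for each endpoint, and the Pocock adjustment is described as covering repeated looks, which it does. Each conclusion concerns one event rate and its own goal, and no overall study success is defined that either endpoint could trigger. The study is a single-arm, observational, post-market one. All of this stands, so the point is an improvement to the plan and not an error in it.

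A reader might also infer three stronger things, none of which the documents support.

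- *The study-wide error is nearly double 0.025.* The exact figure is 4.17%, or 1.67 times 0.025, and it needs both true rates to sit at their goals. Only the nominal 4.94% comes near double.
- *The sequence costs almost nothing.* That is so for mortality power and for the chance of winning both. At the plan's own 10% mortality, regurgitation loses 4.9 points of power, falls below its stated 99%, and loses much of its chance of an early claim. The REPRISE II rate is more favourable, but it comes from 60 subjects and is not the rate on which the design rests.
- *A regurgitation claim without a mortality claim is false.* It need not be. The outcomes differ, and so do the analysis populations (all enrolled against implanted, section 12.2.1). With mortality at 14% and regurgitation at 10%, a stand-alone regurgitation success has probability 0.99995 × (1 − 0.0219) = 98% and would be correct. The sequence gives up that claim.

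Finally, section 12.3.3 mentions a Statistical Analysis Plan that may be amended. If a separate one exists, a testing order could be there. This point is limited to the supplied text.

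**Conclusion.** The point holds as a worthwhile, inexpensive improvement. The two formal claims each use the full 0.025 without an order, and the chance of at least one false claim is about 4.2% when mortality is 14% and regurgitation 16.5%. That figure assumes independence and full denominators. It varies little with dependence (3.9% to 4.2%) or with an assumed 80% to 95% evaluable for regurgitation (4.2% to 4.5%). A mortality-first sequence brings the worst case to about 2.2% at no cost to the primary endpoint. The price falls on the secondary claim: about 5 points of power at the planning rates, more if true mortality exceeds 10%, and almost none if it is well below. The documents do not support calling this a breach of a promised error rate.

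**What to change.** In section 12.3.2 and the synopsis Success Criteria, state that regurgitation is formally tested, at the same look-specific levels, only at or after the look at which the mortality null is rejected. Otherwise it is reported descriptively with its confidence bound. This should be settled before the first look.

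The text change is small, but two consequences must be written down with it:

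- The power above 99% in section 12.1.2.2, and in the matching synopsis entry, should be restated as about 95.1% at the planning rates, with its dependence on true mortality.
- The plan should say that no formal regurgitation claim is available if the mortality goal is missed, and that interim regurgitation claims wait for mortality.

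If the sponsor prefers two separate claims, it should say so and state that error is not controlled across them.
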